Outcomes:	
Primary outcome:
 
The Desirability of Outcome Ranking (DOOR) developed for this study comprises five ranks (Table 1) and is assessed at day 90. The primary outcome will be expressed as the win ratio, i.e., the ratio of the number of times that participants in the intervention group have a lower DOOR compared to those in the control group. In this study, we use the win ratio approach of Pocock et al. (2012), i.e., every participant in the linezolid group is compared with every participant in the control group. When comparing two participants, the winner will be determined by the first component of the DOOR in which the two participants differ, the only exceptions being ties when both participants die or if they do not die but have the same length of hospitalisation (see section 11 STATISTICAL METHODS for details).
 
  
 Rank	Alive at 90 days	Return to usual level of function by day 90	None of the following complications:	Hospital length of stay	
   
 1	Yes	Yes	Yes (no complications occurred)	Ties will be resolved using the length of hospitalisation	
 
 2	Yes	Yes	No (complication occurred)	
 
 3	Yes	No	Yes (no complications occurred)	
 
 4	Yes	No	No (complication occurred)	
 
 5	No	Not applicable	Not applicable	Not applicable	
  
	Rank	Alive at 90 days	Return to usual level of function by day 90	None of the following complications:	Hospital length of stay	1	Yes	Yes	Yes (no complications occurred)	Ties will be resolved using the length of hospitalisation	2	Yes	Yes	No (complication occurred)	3	Yes	No	Yes (no complications occurred)	4	Yes	No	No (complication occurred)	5	No	Not applicable	Not applicable	Not applicable

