2.7 Patient Information and Informed Consent

Patients will be informed about the study by their treating physician and consent will be obtained from each patient. Patients who are conscious and capable of making decisions will be approached to give their consent. The local investigator (or a designated physician) will explain the nature of the study, its purpose, the procedures involved, the expected duration, the potential risks and benefits and any discomfort it may entail. Each patient will be informed that the participation in the study is voluntary, that the patient may withdraw from the study at any time and that withdrawal of consent will not affect the patient's subsequent medical assistance and treatment. The patient will be informed that any questions can be asked, and that consulting family members, friends, their treating physicians, or other experts before deciding about study participation is possible. Enough time will be given before making the decision about study participation. However, it will be noted that the potential effect of the study medication (i.e. linezolid) might be greater if treatment can be started earlier. The patient will be informed that authorised individuals other than their treating physician may examine the patient's medical records.

Due to the nature of *S. aureus* bacteraemia, we expect approximately 10-20% of patients to be unresponsive and incapable of giving informed consent during the acute infection. These patients are particularly at risk of succumbing to the infection and should thus not be excluded from the study. In these emergency situations, consent will be obtained from the patient's next of kin. If no next of kin are present, an independent physician who safeguards the interests of the patient and is not involved in the conduct of the study can confirm participation ("confirmation by independent physician"). If there is any indication that the patient is unwilling to participate in the study including an advance directive stating such unwillingness, the patient will be excluded from participation. After patients regain capacity of judgement, they will be approached about giving retrospective consent.

We will provide the following specific information sheet and consent forms which will enable an informed decision about study participation:

- 1) Patient informed consent form
- 2) Next of kin informed consent form
- 3) Confirmation by Independent physician

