7.3 Assignment to study groups

Participants will be allocated 1:1 to either linezolid for 5 days or placebo for 5 days. The randomisation will be stratified by centre and ICU status at time of enrolment and done using block randomisation with varying random block sizes of 2 or 4. The trial statistician will generate the randomisation list outside of the data capture system REDCap®. This list will then be uploaded into the data capture system. The goal is to randomise participants such that the groups are as balanced as possible with respect to study centre and ICU status at time of enrolment.

After informed consent has been obtained and all eligibility criteria have been reviewed and met, the local investigator (or designated staff) enters the minimal required data into REDCap® (i.e., participant ID, year of birth, if participant is on ICU). The allocation is done by REDCap® which will display a unique, randomisation number that remains the same throughout the study. Each randomisation number will correspond to a drug container which is labelled with the unique randomisation number.

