9.3.4 Assessment of baseline characteristics (day 1)

Most study-specific baseline characteristics are assessed as part of the clinical routine and can be extracted from the patient charts of each centre. The baseline characteristics include date of hospital admission, index blood culture, linezolid susceptibility, ethnicity, vital signs, polymicrobial bacteraemia (defined as more than one organism [at species level] in the index blood cultures, excluding those organisms judged to be contaminants by the treating clinicians), comorbidities, standard antibiotic treatment, markers of severity (mechanical ventilation, cardiac arrest, use of vasopressors, ICU), labour force status, injection drug use, and mental health diagnosis. The data closest to the time before start of the study treatment should be used. The study team of each site will check at the time of randomisation if all relevant information is available from the clinical routine assessment and – if necessary – will add the missing information by contacting the treating team or the participant directly. Together with the participant, the local investigator (or a delegated physician) will assess the level of function 4 weeks before randomisation. In case the participant is not able to provide this information, this data will be assessed at day 90 (asking about their level of function 4 weeks before their *S. aureus* bacteraemia).

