11.2 Determination of Sample Size

We collected retrospective data on the DOOR components from all *S. aureus* bacteraemia patients treated at the University Hospital Basel in 2022 (n=119). Our assumptions for the sample size are based on these data along with what is known from the literature to derive plausible estimates for the DOOR components. Patients who died in the first three days after a *S. aureus* bacteraemia diagnosis were excluded so that we do not overestimate the mortality of the planned trial (of note, most of these patients would probably have died before they could have been included in our study ($n = 8$)). Following extensive consultations with patient representatives, we have established that, for mortality at 90 days, a trial should demonstrate a meaningful relative difference of 10% (equating to an absolute difference of 2.2%). Meanwhile, for the remaining domains, the following relative reductions were deemed acceptable: 15% for level of function and 20% for complications and length of hospital stay).

The sample size was calculated using a simulation approach, for which 1000 synthetic datasets for each combination of plausible values for the relevant parameters were generated. We calculated the p -value of the win ratio for each of the simulated datasets and tested for statistical significance at $\alpha = 0.05$ using the unmatched win-ratio approach described in Pocock et al.¹¹⁷. The final sample size is based on the following specific assumptions:

- The statistical tests are conducted at a two-sided significance level of $\alpha=0.05$, and the desired power is 90%
- The two treatment arms are equal in size (1:1 allocation)
- The proportion of deaths within 90 days in the control group is expected to be 22.5% and 20.3% in the linezolid group (relative reduction of 10%; absolute reduction of 2.2%)
- The proportion of participants with worse level of function in the control group is expected to be 25.0% ²¹, and 21.3% in the linezolid group (relative reduction of 15%; absolute reduction of 3.7%)
- The proportion of participants with any complications (defined DOOR component) will be 6.3% in the control group and 5.0% in the linezolid group (relative reduction of 20%; absolute reduction of 1.3%).

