11.4 Planned Analyses

11.4.1 Datasets to be analysed, analysis populations

Analyses will be performed on the full analysis set (i.e., all randomised participants) and the per protocol dataset

(i.e., those who received at least 7 out of 10 doses of linezolid or placebo). The primary estimand to be calculated in this study is the effect (summarised as the win ratio) of being randomly assigned to treatment with linezolid in the patient population (i.e., equivalent to an intention-to-treat analysis). We will also estimate the treatment effect among the treated participants (i.e., the per protocol dataset).

A detailed analysis plan will be written before closing the study database. Of note, we are currently conducting a systematic scoping review, assessing current practices how to analyse a hierarchical composite outcome. These results will inform our pre-specified analysis plan. Furthermore, we will consider further developments in risk-score classifications for *S. aureus* bacteraemia (e.g. for a potential use of a matched win-ratio versus unmatched win-ratio). The statistical analysis plan will be made publicly available (on clinicaltrials.gov). Currently we intend to conduct the following analyses:

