11.4.2 Primary Analysis

Treatment and placebo will be compared on the basis of the win-ratio approach as described by Pocock and colleagues:¹¹⁷ In brief, each participant in the treatment group will be compared with each participant in the placebo group. When comparing two participants, the winner will be determined by the first component of the DOOR in which the two participants differ. The following two scenarios will be considered as a tie: (i) when both participants died within 90 days, or (ii) when participants have the same outcomes for all DOOR elements, including length of hospital stay. The win ratio will be calculated by dividing the number of cases in which participants receiving linezolid win compared with the number of cases in which participants receiving placebo win. We will reject the null hypothesis that the win ratio is equal to 1 if the *p*-value is less than 0.05.

Subgroup analyses: For the primary outcome and for all DOOR components separately, we will assess if treatment effects differ by sex (male vs. female), ICU status at baseline (participants on ICU vs. participants not on ICU) and focus of infection (vascular catheter, skin and soft tissue, endocarditis, osteoarticular, pneumonia, other focus, or focus not identified). All subgroup analyses will be exploratory in nature.

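### Randomisation is stratified by ICU status and centre, but the primary win ratio uses neither: the test is valid, and somewhat conservative if ICU status is prognostic

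*Protocol*

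**What the plan says.** On the design, Protocol section 7.3 states: "The randomisation will be stratified by centre and ICU status at time of enrolment". It uses blocks of 2 or 4 and aims to randomise "such that the groups are as balanced as possible with respect to study centre and ICU status at time of enrolment".

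On the primary analysis, section 11.4.2 says that "each participant in the treatment group will be compared with each participant in the placebo group", and the synopsis (Outcomes) likewise that "every participant in the linezolid group is compared with every participant in the control group". Section 11.2 sized the trial "using the unmatched win-ratio approach". ICU status enters the primary outcome only as an exploratory subgroup.

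The secondary regression models in section 11.4.3 do adjust for ICU status and centre, together with sex.

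Section 11.4.1 describes the analyses as current intentions. A detailed plan is to follow, informed by a scoping review "assessing current practices how to analyse a hierarchical composite outcome" and possibly by matching on a risk score. The randomisation strata are not mentioned there.

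**The concern.** Stratified blocks remove most chance imbalance between arms in ICU status. If ICU status predicts the outcome, the true variance of the net wins is then smaller than the all-pairs variance formula assumes, because that formula treats between-stratum differences as random noise between arms. The test statistic is too small on average, the actual type I error falls below 5%, and some power is lost.

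The protocol gives reason to expect ICU status to be prognostic. Section 9.3.4 includes it among "markers of severity (mechanical ventilation, cardiac arrest, use of vasopressors, ICU". Section 2.7 expects 10-20% of patients to be unresponsive and says of them: "These patients are particularly at risk of succumbing to the infection". That second group is not the same as the ICU group, so it is only indirect support.

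What is at stake is efficiency. The validity of the test is not in doubt.

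**Working it through.** **1. The plan's own figure.** Section 11.2 gives 550 participants for 90% power at two-sided 0.05, raised by 10% (550 × 1.10 = 605, or 606 as an even number). The 550 cannot be reproduced exactly, because the mean and SD of the log-normal length-of-stay (LOS) model are not given. With assumed medians of 10 to 20 days and log-SDs of 0.6 to 1.0, taking 20% off the mean of log LOS gives 86% to 100% power at 550. Reading the 20% as a 20% shorter stay (median 15 days) gives 54% to 75%. The comparison below was therefore calibrated so that the pooled test has about 90% power.

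**2. Inputs from the protocol.** N=550; control rates 22.5% death, 25% worse function, 6.3% complications; relative reductions 10/15/20%, applied equally in both ICU strata; missing data 10% for function and 3% for the other components, moving to the next domain; about 12 centres; blocks of 2 or 4 within centre and ICU status.

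**3. Assumed inputs.**
- Unequal centres, with 20% down to 2% of patients.
- Median LOS 14 days in non-ICU controls, SD of log LOS 0.7, and a complication adding 0.3 to log LOS.
- LOS effect ×0.68 to ×0.70, from the calibration.
- ICU shares and ICU effects as listed below, keeping the overall control rates at the protocol values. Example for scenario 5: 0.25 × 40% + 0.75 × 16.7% = 22.5%.
- A moderate centre effect means between-centre SDs of 0.3 (logit death), 0.3 (logit function) and 0.2 (log LOS). A large one means 0.5/0.5/0.35.

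**4. Test.** Let U_i be participant i's wins minus losses, T the sum of U_i over the linezolid arm, and V = n1·n0 / (N(N−1)) × ΣU_i². The pooled test is z = T/√V. The ICU-stratified test is z = Σ(T_s/N_s) / √Σ(V_s/N_s²), with U_i formed within stratum.

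**5. Scenarios** (ICU vs non-ICU controls)
1. No ICU effect, 20% ICU.
2. Death only, 25% ICU: death 40 vs 16.7%.
3. Mild, 20% ICU: death 35 vs 19.4%, worse function 35 vs 22.5%, LOS ×1.25.
4. Moderate, 15% ICU: death 40 vs 19.4%, function 40 vs 22.4%, LOS ×1.5.
5. Moderate, 25% ICU: death 40 vs 16.7%, function 40 vs 20%, LOS ×1.5.
6. Extreme, 30% ICU: death 45 vs 12.9%, function 50 vs 14.3%, LOS ×2.

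**6. Results** (pooled, then ICU-stratified)

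| Scenario | Power %, no centre effect | Change in power, moderate centre effect (points) | Type I error %, no centre effect | Size-adjusted gain (points) | Median win ratio |
|---|---|---|---|---|---|
| 1 | 90.1, 90.0 | −0.2 | 4.8, 4.9 | 0.1 | 1.40, 1.40 |
| 2 | 90.8, 91.7 | +0.7 | 5.2, 5.5 | 0.4 | 1.41, 1.42 |
| 3 | 90.2, 91.0 | +0.4 | 4.8, 5.2 | 0.0 | 1.40, 1.41 |
| 4 | 89.3, 90.5 | +1.1 | 3.7, 4.6 | 0.0 | 1.39, 1.41 |
| 5 | 90.0, 92.2 | +2.1 | 4.4, 5.6 | 0.6 | 1.40, 1.43 |
| 6 | 90.3, 95.3 | +4.5 | 2.8, 4.9 | 1.3 | 1.38, 1.47 |

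Power used 2,600 paired datasets per cell (SE of the difference 0.16 to 0.43 points). Type I error and size-adjusted power used 4,000 per cell, or 2,600 for scenario 4 (SE about 0.35 to 0.4 points). Scenario 4 gave 4.4 and 4.8% once a centre effect was added, so only scenario 6 is clearly and repeatedly below 5%.

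**7. Repeats under other assumed values.** With 20% to 30% ICU, ICU deaths of 30% to 45%, median LOS 10 days, log-SD 0.95 and no missing data, the pooled type I error was 5.4% (no effect), 4.1% (mild), 3.7% (moderate) and 2.9% (strong). Power moved from 85.2 to 85.3, 86.5 to 86.7, 84.4 to 85.9 and 84.7 to 89.7%. A further repeat, without missing data, gave changes of −0.4, +0.6, +2.6 and +5.6 points for none, mild, moderate and extreme.

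**8. Adding centre.** Compared with ICU strata alone, ICU × centre cells changed power by −0.6 to −2.2 points with no centre effect, +0.2 to +0.9 with a moderate one and +1.7 to +2.9 with a large one (scenario 4 not run for the large effect). Weighting matters: over all 24 cells, giving every pair equal weight cut power to 68% to 82%, while weights of 1/(n+1) kept it at 84% to 90%.

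**9. Pairs not used.** Cross-stratum pairs are 1 − (p² + (1−p)²) of the total: about 26%, 32%, 38% and 42% at p = 15%, 20%, 25% and 30% ICU.

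**The case against.** The best counter-argument is that nothing here is an error. The synopsis, section 11.2 and section 11.4.2 describe the same unmatched test, and stratified randomisation does not contradict it. Section 11.4.1 leaves room for the later plan to change the method. The secondary analyses adjust only the regressions and leave the Wilcoxon tests for SF-36 unadjusted, so an unadjusted rank-type primary fits that pattern. The gain is small: with both tests held to the same actual error rate it is 0 to 0.6 points in plausible scenarios. Every ICU figure is assumed. The remedy also changes the estimand and leaves many pairs unused.

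Most of this stands as a limit on the size of the point, but it does not remove it. The protocol is not silent: it states the all-pairs comparison twice, and the only alternative it names is risk-score matching. Section 11.4.6 requires an amendment for substantial deviations, and a change of primary estimand could well count as one. The size-adjusted comparison shows where the gain comes from, but the sponsor cannot size-adjust the pooled test in practice. Stratifying is a direct way to use the full 5%.

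**Conclusion.** The concern holds as a modest loss of efficiency. The planned test is valid and consistent with its sample size calculation. If ICU status is prognostic, ignoring it gives up about 0.5 to 2 points of power near 90% in plausible scenarios, and about 5 in an extreme one. If it is not prognostic, ICU stratification costs between nothing and about 0.4 points.

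These figures rest on assumed ICU shares, ICU-specific rates, LOS distribution and centre variation, since the protocol gives none of them. The difference between the pooled and within-stratum win ratios (at most 1.38 against 1.47, in the extreme scenario) reflects two estimands and is not bias.

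**What to change.** Suggested text for section 11.4.2: *The primary win ratio is stratified by ICU status as used at randomisation. Each linezolid participant is compared with each placebo participant in the same ICU stratum. Wins and losses are each divided by the stratum size N before summing over strata (weights n1·n0/N for the net wins), with the matching within-stratum variance, and win ratio = 1 is tested at two-sided 0.05.*

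- Reword the estimand in section 11.4.1 and the synopsis as the win ratio between participants of the same ICU status at enrolment.
- Report the unstratified all-pairs win ratio as a sensitivity analysis.
- Add a sentence in section 11.2, and where the synopsis refers to it, that the sample size was simulated with the unstratified test.
- Decide in the analysis plan, before unblinding, whether to add centre or pooled centres. If so, do not give every pair equal weight across small cells.
- If the all-pairs test is kept as primary, give the reason.

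The cost is wording only, with no new data and no change to the sample size. The ICU subgroup analysis already needs the within-stratum comparisons. The downsides to state are the changed estimand and the unused cross-stratum pairs.

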11.4.3 Secondary Analyses

We intend to conduct the following analyses for the secondary outcomes:

Logistic regression

- Returning to usual level of function by day 90
- Microbiological treatment failure 14-90 days after randomisation
- Early microbiological treatment failure 5-13 days after randomisation
- Clinical treatment failure 14-90 days after randomisation
- Persistent bacteraemia defined as positive blood culture on day 5 after randomisation
- Meeting two or more SIRS criteria simultaneously on day 5 after randomisation

Log-normal linear regression

- Length of hospital stay of acute index inpatient hospitalisation (in days)

Poisson regression

- Number of days without being on the Intensive Care Unit (ICU) up to day 90
- Number of days alive and free of antibiotics up to day 90

Cox proportional hazards model

- Time to death up to day 90

Fine & Gray competing risk model

- Time to being discharged alive (assessed until day 90)

The models listed above will include sex, ICU stay at baseline, and centre as adjustment factors (will be further pre-specified in separate data analysis plan).

Wilcoxon-Mann-Whitney test

- Physical health at day 90 as assessed by the short form 36 (SF-36) questionnaire
- Mental health at day 90 as assessed by the short form 36 (SF-36) questionnaire

Subgroup analyses: We will conduct the following subgroup analyses on the primary outcome to assess if treatment effects differ by sex (male vs. female), ICU status at baseline (participants on ICU vs. participants not on ICU), and dominant focus of infection (vascular catheter, skin and soft tissue, endocarditis, osteoarticular, pneumonia, other focus, or focus not identified).

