9.2.2 Assessment of secondary outcomes

The secondary outcomes include each part of the DOOR outcome separately as described in chapter 9.2.1 *Assessment of primary outcome* and time to death up to day 90.

Further secondary outcomes will be assessed as follows:

Clinical outcomes:

- Time to being discharged alive (assessed until day 90)

In the eCRF, we collect the day of hospital discharge (see 5.1 *Primary Outcome* for detailed definition of primary outcome). For participants who die during the hospitalisation, 90 days will be recorded.
- Number of days without being on the Intensive Care Unit (ICU) up to day 90 (i.e. mean number of days being alive without being on the ICU between randomisation until day 90).

After day 90 we will collect from the hospital information system data how many days the participant spent on the ICU. Together with the available data on mortality, we will calculate the "Number of days without being on the ICU".

Infection dynamics and control:

Information on these outcomes is collected from the hospital information system data.

- Persistent bacteraemia: positive blood culture on day 5 (± 1 day) after randomisation. If blood culture on day 2 or 3 is negative, then day 5 blood culture will be assumed to be negative (in case it is not carried out).
- Two or more systemic inflammatory response syndrome (SIRS) criteria on day 5 after randomisation. This includes: 1. Abnormal body temperature ($<36^{\circ}\text{C}$ or $>38^{\circ}\text{C}$), 2. tachypnoea or mechanical ventilation (RR >20 breaths per minute), 3. tachycardia (HR >90 beats per minute in an adult), 4. abnormal leukocyte count (from routine blood sampling on day 5 ± 1 day, defined as $>12.0 \times 10^9/\text{L}$ or $<4.0 \times 10^9/\text{L}$ or $>10\%$ of immature (band) forms).
- Change in C-reactive protein (CRP) from randomisation until day 5 (± 1 day). Day 1 CRP means any blood CRP measurement taken on randomisation day 1 or the calendar day prior to randomisation. If there is more than one measurement, the value recorded is the one taken closest before randomisation.
- Early clinical treatment failure between 5 and 13 days after randomisation leading to treatment change. Newly identified focus of *S. aureus* between 14 and 90 days after randomisation as determined by the site investigator. This can incorporate clinical, radiological, microbiological, and pathological findings.

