11.4.6 Deviation(s) from the original statistical plan

If substantial deviations of the analysis as outlined in these chapters are needed for whatever reason, the protocol will be amended. All deviations of the analysis from the protocol or from the detailed analysis plan will be listed and justified in a separate chapter of the final statistical report.

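### Unqualified Poisson regression for ICU-free and antibiotic-free days: with its default standard errors the intervals would be roughly 1.6 to 3.6 times too narrow

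*Protocol*

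**What the plan says.** Protocol section 11.4.3 lists two outcomes under "Poisson regression": "Number of days without being on the Intensive Care Unit (ICU) up to day 90" and "Number of days alive and free of antibiotics up to day 90". The models adjust for sex, ICU stay at baseline and centre. The section mentions neither overdispersion nor a method for the standard errors.

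Section 9.2.2 explains the ICU outcome as the "mean number of days being alive without being on the ICU between randomisation until day 90". Both outcomes therefore lie between 0 and 90 days and are cut short by death. On mortality, section 11.2 states: "The proportion of deaths within 90 days in the control group is expected to be 22.5% and 20.3% in the linezolid group".

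The list of analyses is provisional. Section 11.4.1 introduces it with "Currently we intend to conduct the following analyses" and adds: "A detailed analysis plan will be written before closing the study database". Section 11.4.6 gives the protocol text some weight of its own: "If substantial deviations of the analysis as outlined in these chapters are needed for whatever reason, the protocol will be amended".

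**The concern.** Poisson regression in its standard form takes the variance of the outcome to equal its mean, and its model-based standard errors rest on that. Here most participants have a high value and roughly one in five, those who die, form a long low tail. The variance must then be well above the mean.

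If the model is run as named, with default standard errors, the confidence intervals for both outcomes will be too narrow. A chance difference in either direction could then be read as an effect of linezolid on ICU or antibiotic burden. A larger sample would not help, because the error does not shrink with sample size.

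**Working it through.** **Plan's own figure.** The protocol gives no dispersion or error rate for these models. The nearest stated figure is the sample size: 550 × 1.10 = 605, rounded up to an even 606, or 303 per arm (section 11.2). This reproduces.

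**Inputs from the protocol.** Mortality m is 20.3% and 22.5% (11.2), midpoint 21.4%. There are about 12 centres (synopsis). Antibiotic courses last at least 2 to 6 weeks (8.7). Death timing comes from Table 2 in section 3.1: the levofloxacin trial reports 28-day mortality of 14% in both arms and 90-day mortality of 18% and 21%. So 14/21 = 67% to 14/18 = 78% of its deaths fell by day 28.

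**Step 1: death only.** Let D be days alive to day 90 and L the days lost by a participant who dies.
- Mean of D = 90 − m·E(L)
- Variance of D = m·E(L²) − m²·E(L)²
- φ = variance / mean

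The true variance of the log ratio of two arm means is φ times the model-based variance, and the number per arm cancels. Standard errors are therefore √φ times too small, and the true two-sided error rate at nominal 5% is 2·(1 − Φ(1.96/√φ)).

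Three timings were used:
- Even over 0-90 days: E(L) = 45, E(L²) = 2700.
- Table 2, spread evenly within days 0-28 and 28-90. With 67% by day 28: E(L) = 61, E(L²) = 4321. With 78%: E(L) = 66, E(L²) = 4828.
- No death before day 30: E(L) = 30, E(L²) = 1200.

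| Timing | m | Mean | Variance | φ | √φ | Error rate |
|---|---|---|---|---|---|---|
| Even | 20.3% | 80.9 | 465 | 5.75 | 2.40 | 41% |
| Even | 22.5% | 79.9 | 505 | 6.32 | 2.51 | 44% |
| Table 2, 67% | 20.3% | 77.6 | 724 | 9.33 | 3.05 | 52% |
| Table 2, 78% | 22.5% | 75.2 | 866 | 11.5 | 3.39 | 56% |
| None before day 30 | 20.3% | 83.9 | 207 | 2.46 | 1.57 | 21% |
| None before day 30 | 22.5% | 83.3 | 224 | 2.70 | 1.64 | 23% |

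With even timing and lower mortality the rate is still 35% (m = 15%) and 25% (m = 10%).

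**Step 2: the two outcomes, adjusted.** Trials with no treatment effect were simulated with 606 participants and a Poisson model on arm, sex, ICU and 12 centres. The following are assumptions, not protocol figures, and were varied:
- ICU share 25% (10-40%)
- ICU stay log-normal with median 5 days (3-10)
- death risk in ICU patients doubled (×1 to ×4)
- antibiotic courses uniform over 14-42 days (also 28-42, and 14 only)

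Results with model-based standard errors:
- m = 20.3-22.5%, even or Table 2 timing: standard errors 2.3-3.6 times too small, 38-60% nominally significant.
- m = 21.4%, no death before day 30: 1.7-2.3 times, 23-39%.

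Under these assumptions the covariates removed at most about 11% of the dispersion.

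**Step 3: effect on the interval.** At a ratio of 1, m = 21.4% and Table 2 timing, the upper 95% limit for ICU-free days is +1.9% model-based against +6.1% robust. For antibiotic-free days it is +2.3% against +7.9%. With even timing the pairs are +1.8% against +4.5%, and +2.2% against +6.3%.

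**Step 4: the repair.** With the same mean model and covariates, quasi-Poisson errors gave 3.0-5.8% and sandwich errors 4.0-5.9% in every scenario. A second set of simulations with other death timings gave 4.1-5.3% and 4.7-7.2%.

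**The case against.** The strongest reply is that the protocol names only a regression family, and the choice of variance estimator belongs in the analysis plan. The list is a current intention, a detailed plan is promised, and 11.4.3 itself defers further specification of the models to it. That plan may already use robust errors. This stands in part, and it makes the finding conditional. It does not remove it: an unqualified Poisson regression denotes variance equal to mean, and a plan that copies the protocol literally inherits the problem.

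A second reply is that the percentages depend on when deaths occur. This stands. The upper part of the range assumes that the death timing of one open-label trial carries over to this one. Section 3.1 also says 40-60% of deaths come after the initial infection, without giving days. Later deaths lower the figures, but no scenario tried came near 5%. Scoring every death as zero days would raise them to 61-66%, but the outcomes count days alive, so that case is left out.

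A third reply is that little depends on these outcomes. This also stands. The secondary objectives are exploratory, 11.4.3 sets no significance threshold, and the only stated rejection rule is for the win ratio.

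A reader might go further and infer that Poisson regression must be replaced, or that the trial will report false effects in 38-60% of such comparisons. The documents support neither. Poisson can stay as the model for the mean, and the error rates arise only if model-based standard errors are used, which the protocol does not say.

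**Conclusion.** The concern holds in conditional form and should be fixed. Run with default model-based standard errors, the model named for these two outcomes would give intervals roughly 1.6-3.6 times too narrow and call about 21-60% of null comparisons nominally significant. The range is about 38-60% if deaths are evenly spread or follow the Table 2 trial, and about 21-39% if none occurs before day 30. These figures rest on the protocol's mortality and on assumed death timing; the adjusted simulations also rest on assumed ICU use and antibiotic duration.

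The consequence is confined to two exploratory secondary outcomes. The primary win ratio, the sample size and the DSMB reviews are untouched. Confidence is medium, because the analysis plan may already settle the point.

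**What to change.** State in the analysis plan, before database closure, that the models for ICU-free days and antibiotic-free days use quasi-Poisson (dispersion-scaled) or sandwich standard errors, and name which. Preferably add the same clause to 11.4.3. The Poisson mean model and the covariates stay as they are, so this is compatible with the protocol and need not count as a substantial deviation under 11.4.6. Quasi-Poisson stayed slightly closer to 5% at the upper end of the simulations (at most 5.8%, against 7.2% for sandwich errors).

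The cost is wider, approximately correctly sized intervals: about 2.3-3.6 times wider under even or Table 2 timing, and less if deaths come later. Editing 11.4.3 also means a minor protocol amendment. No extra data or participants are needed.
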